6.0 Number of Subjects

Sample size of n=25 patients in the Patient Navigation Group and n=25 patients in the Usual Care Group.

Patients who meet eligibility criteria and provide informed consent to participate in the LPNP will be enrolled up to the sample size goal of 25 patients. Upon completion of all study visits for the Patient Navigation Group, 25 additional patients who meet the inclusion criteria will be identified through the CCCR biorepository study to be included in the Usual Care group. Healthcare utilization and medication compliance data will be provided via a formal request (see Sections 12 & 13 below) to the CCCR and provided to study staff.

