5.0 Inclusion and Exclusion Criteria / Study Population

Criteria for Inclusion:

INTERVENTIONAL GROUP (n=25): 1) Self-identified Minority. 2) Patients ≥ 18 years of age as documented in the electronic medical record. 3) Meeting either American College of Rheumatology or SLICC Classification Criteria for SLE as documented in the electronic medical record (12, 13). 4) Ability to speak and understand English by self-report. 5) In the past six months having ≥ 1 missed clinic or diagnostic study/laboratory visit as documented in the electronic medical record, self-reported failure to adhere with prescribed medical therapy for SLE, or the participant is newly diagnosed with SLE. 6) In the past six months having been prescribed at least one immunosuppressive medication for SLE activity as documented in the electronic medical record regardless of whether taking the medication. 7) Have telephone access.

USUAL CARE GROUP (n=25): Meet criteria 1, 2, 3, 5, 6, 7 above for interventional group. All data from healthcare utilization and medication compliance will be collected via the CCCR biorepository request process. See data collection guidelines for this group below (Sections 12 & 13).

Criteria for Exclusion (Interventional Group only): 1) Unwilling or unable to give informed consent. 2) Being a prisoner or institutionalized individual. 3) Without telephone access. 4) Do not meet all of the inclusion criteria listed above.

Criteria for Exclusion (Usual Care Group only) 1) Do not meet usual care inclusion criteria above.

Recruitment will be enhanced by MUSC having specialized lupus clinics already in place dedicated to the care of patients with SLE.

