8.0 Recruitment Methods

The patient's primary rheumatologist can refer the patient to the PI/study staff for eligibility review after discussing with the patient. If needed, Epic (EMR) rheumatology-specific clinic schedules and charts of those patients seeing those rheumatologists (PI/Co-I) will be reviewed weekly for patients with lupus and self-identified as a minority. These patients will be contacted by PI/Study Staff only if they not opted out for research contact. Additionally, outreach and advertising materials will be used to promote and introduce the study to potential candidates. Material will be made available to PI/Co-I's for discussions with pts, within MUSC Rheumatology Clinic waiting rooms for pt initiated access/interest, as well as hardcopy and electronic versions (email) to potential pts as appropriate following preferred communication method of the pt as noted in Epic. Outside of any direct in-person exchange/presentation, there will be an accompanying notification that explains the contact (i.e. brochure). Eligibility will be confirmed by the PI. Subjects will be contacted via telephone and/or at their clinic visit.

We do not anticipate difficulty enrolling 25 patients into the LPNP intervention group within the initial eight months of the 24-month funding period, given the large number of high-risk patients followed at MUSC. For example, based on recent experience and EMR administrative data review, at least 35% of the 1320 patients with SLE followed at MUSC in the last two years meet the demographic (age, race, disease duration) and medication criteria.

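### No index date is defined for usual-care patients; a six-month look-back counted from identification would fall inside or after any retrospective outcome window

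*Combined protocol and SAP*

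**What the plan says.** Four parts of the plan bear on the timing of the usual-care group.

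- **When controls are found.** Section 6.0: "Upon completion of all study visits for the Patient Navigation Group, 25 additional patients who meet the inclusion criteria will be identified". The source is the CCCR biorepository study.
- **What they must satisfy.** Section 5.0: "Meet criteria 1, 2, 3, 5, 6, 7 above for interventional group". Criterion 5 can be met by a missed visit ("In the past six months having ≥ 1 missed clinic or diagnostic study/laboratory visit as documented in the electronic medical record") or by one of two other routes ("self-reported failure to adhere with prescribed medical therapy for SLE, or the participant is newly diagnosed with SLE"). Criterion 6 reads: "In the past six months having been prescribed at least one immunosuppressive medication for SLE activity". The criteria are imported by number, and the six months are not re-anchored for this group.
- **What data they contribute.** Section 6.0: "Healthcare utilization and medication compliance data will be provided via a formal request". The usual-care paragraph of Section 10.0 adds that the analysis uses standard-of-care data that exist already, which is why no separate consent is taken.
- **How they are compared.** Section 12.0 reports outcomes at baseline and at 3, 6 and 12 months. It adjusts for baseline covariates such as age and SLEDAI by propensity weighting and mixed models, and compares the groups monthly over 12 months.

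Navigator patients have a baseline visit in the Section 10.0 schedule. For usual care, Section 5.0 refers the reader to Sections 12 and 13. Section 12.0 gives no start date for these patients, and Section 13.0 deals with confidentiality and storage.

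**The concern.** Every planned comparison needs a month 0 for each control: the time-point summaries, the monthly comparison and the baseline covariates. Without one, two honest brokers following the same text could extract different cohorts and different follow-up periods.

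The missing date also affects who is selected. Navigator patients meet criteria 5 and 6 before their follow-up starts. If staff apply the same words on the day controls are identified, controls meet them during or after the year being analysed. Eligibility in one arm would then depend on events after baseline. Weighting on baseline covariates does not remove that kind of difference, least of all when the control baseline has no date.

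Stated outcomes are involved. A missed clinic or laboratory visit is one entry route, and adherence with visits and laboratory appointments is a secondary outcome in Section 12.0. Whether that outcome is collected in usual care is unclear: Sections 5.0, 6.0 and 10.0 name only utilization and medication data for this group, while Section 12.0 promises everything in Sections 4.0 and 10.0. Criterion 6 selects on a recent prescription, which bears on being in care and so on medication adherence, the primary outcome.

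**Working it through.** The plan gives no figure to reproduce here. The check is a timeline built from its own durations.

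**Inputs**
- Enrolment of 8 months and funding of 24 months: Section 8.0 ("within the initial eight months of the 24-month funding period").
- Navigator follow-up of 12 months: Sections 10.0 and 14.0.
- Look-back of 6 months: Section 5.0.
- Assumed: enrolment opens at month 0 of funding, and identification comes *d* months after the last navigator visit. The documents give no delay; *d* = 0 follows Section 6.0 most closely.

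**Step 1: the look-back if counted from identification.** The last navigator visit is at 8 + 12 = month 20. With *d* = 0 the look-back is months 14 to 20.

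**Step 2: possible usual-care outcome windows**

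| Outcome window | Months | Overlap with look-back | Look-back after window |
|---|---|---|---|
| Year just ended | 8–20 | 6 | 0 |
| Matched, start at month 0 | 0–12 | 0 | 6 |
| Matched, start at month 2 | 2–14 | 0 | 6 |
| Matched, start at month 4 | 4–16 | 2 | 4 |
| Matched, start at month 6 | 6–18 | 4 | 2 |
| Matched, start at month 8 | 8–20 | 6 | 0 |
| Forward from identification | 20–32 | 0 | 0 |

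In every row that ends by month 20, the look-back lies inside the window, after it, or partly in each. The forward row puts the look-back before the window, but it ends 32 − 24 = 8 months after funding and does not fit a group analysed on existing data.

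**Step 3: average overlap with matched windows.** For start *s* between 0 and 8, overlap = max(0, *s* − 2 − *d*). With *s* uniform and *d* no more than 6, the mean is (6 − *d*)²/16:
- *d* = 0: 36/16 = 2.25 months
- *d* = 2: 16/16 = 1.0 month
- *d* = 4 (month 24, end of funding): 4/16 = 0.25 month
- *d* = 6: 0

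This is not reassurance. As overlap shrinks, the look-back moves past the end of follow-up, and controls then qualify on what happened after their outcomes. Under the year-just-ended reading the overlap is 6 months whatever the delay.

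**Step 4: with an index date *t*.** If the look-back runs from *t* − 6 to *t* and outcomes from *t* to *t* + 12, the overlap is 0, as in the navigator group.

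**Illustration only, all inputs assumed:** with 4 appointments per six months, 20% missed, intra-patient correlation 0.15 (beta-binomial), every patient entering by a missed visit, the year-just-ended window and no true effect, criterion 5 alone gives 28.0% missed in the navigator group against 33.7% in usual care, a gap of 5.7 points (2.0 to 12.3 over 3, 4 or 6 appointments, 10% to 30% missed and correlation 0.05 to 0.30).

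**The case against.** The best counter-argument is that staff will back-date eligibility. Section 5.0 applies the same criteria to both groups, navigator patients are screened before baseline, and Section 12.0 speaks of a baseline in the analysis. The new-diagnosis route points the same way: if it also means within the six months, a control entering by it could not supply a prior year of lupus treatment data. On that reading nothing overlaps. This stands as a plausible intention, but no section states it.

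A forward window is also conceivable, since part of the usual-care paragraph in Section 10.0 describes collection as ongoing quality monitoring. The same paragraph ends by relying on existing data, and the window would outrun the funding, so this reading is hard to sustain.

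The illustration is not evidence about this trial. It concerns a secondary outcome that may not be collected in usual care, and entry by the other two criterion 5 routes would generally dilute the gap. It is also small against sampling error. With 8 appointments per patient, about 30% missed and correlation 0.15, the standard error of the difference is roughly √(2 × 0.30 × 0.70 × (1 + 7 × 0.15) / (8 × 25)) = 0.066, or 6.6 points.

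Finally, this is a non-randomised, mainly descriptive pilot aimed at feasibility. That limits the consequence. Section 12.0 nevertheless plans weighted group comparisons with effect sizes, claims power for a group difference in adherence, and will use the data to size the next trial.

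**Conclusion.** The point holds as a gap in the definition of the control group: the plan cannot be carried out without choosing a month 0 that it does not give. If the look-back is counted from identification, it overlaps the outcome window by 6 of 12 months (year just ended) or by 0 to 6 months (matched windows), with the remainder after the window. These figures rest on the planned 8-month enrolment, 12-month follow-up and a retrospective window.

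A reader might go further and infer that controls are in fact selected on their own outcomes, and that the comparison is therefore biased towards the navigator. The documents do not support that. They define no usual-care window, so the overlap is conditional. Criterion 6 could favour controls who are still in care and so act against the missed-visit effect. For medication adherence, neither the direction nor the size of any distortion can be worked out from the text. No false-positive rate is claimed.

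This is a cheap improvement, held with moderate confidence, to be settled before the CCCR data request is filed.

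**What to change.** In Sections 5.0 and 6.0 and in the CCCR data request:

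- Assign each usual-care patient an index date inside the navigator enrolment window, by a rule fixed in advance and independent of later data. Matching to the navigator patients' baseline dates is one such rule.
- Apply criteria 5 and 6 only to the six months before that date, measure baseline covariates at that date, and count outcomes only in the 12 months after it.
- Have the honest broker select controls on pre-index data only, and keep those who later stop attending.
- Where numbers allow, require CCCR enrolment by the index date, because joining later is itself a form of selection on follow-up. Otherwise report how many joined after it.

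The cost is wording, slightly more programming by the broker, and possibly a smaller pool of eligible controls. No study visits or increase in sample size are needed. Section 8.0 implies about 0.35 × 1320 = 462 patients meeting the demographic and medication criteria, before criterion 5 and CCCR enrolment are applied. The documents do not say how many of them are in the CCCR, so the size of the final pool should be checked.

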7.0 Setting

MUSC Rheumatology clinics, MUSC inpatient setting

8.0 Recruitment Methods

The patient's primary rheumatologist can refer the patient to the PI/study staff for eligibility review after discussing with the patient. If needed, Epic (EMR) rheumatology-specific clinic schedules and charts of those patients seeing those rheumatologists (PI/Co-I) will be reviewed weekly for patients with lupus and self-identified as a minority. These patients will be contacted by PI/Study Staff only if they not opted out for research contact. Additionally, outreach and advertising materials will be used to promote and introduce the study to potential candidates. Material will be made available to PI/Co-I's for discussions with pts, within MUSC Rheumatology Clinic waiting rooms for pt initiated access/interest, as well as hardcopy and electronic versions (email) to potential pts as appropriate following preferred communication method of the pt as noted in Epic. Outside of any direct in-person exchange/presentation, there will be an accompanying notification that explains the contact (i.e. brochure). Eligibility will be confirmed by the PI. Subjects will be contacted via telephone and/or at their clinic visit.

We do not anticipate difficulty enrolling 25 patients into the LPNP intervention group within the initial eight months of the 24-month funding period, given the large number of high-risk patients followed at MUSC. For example, based on recent experience and EMR administrative data review, at least 35% of the 1320 patients with SLE followed at MUSC in the last two years meet the demographic (age, race, disease duration) and medication criteria.

9.0 Consent Process

IRB approved personnel are authorized and qualified to obtain consent. The informed consent document may be sent to potential subjects prior to scheduling a screening visit, either by mail or email, for their review.

Informed consent will be obtained in a private clinic room. The consent will be explained to the subjects and they may take time to read the document; subjects will be given ample time to review the ICF and ask questions; subject's questions will be answered by the investigator and/or study staff. After signing, subjects will be given a signed/dated copy of the ICF. There is no wait period. No study procedures will be performed prior to obtaining written informed consent.

To reduce barriers to enroll in the study during times of unexpected campus and/or clinic shutdowns (pandemics, weather occurrences, etc.), remote consent option will be available. Participants will have the option to complete consent 1) via MUSC's doxy.me system (tele consent) or 2) via REDCap electronic consent (e-consent) combined with a phone discussion. These procedures for consenting remote study participants are in line with the IRB approved procedures and are supported through MUSC SCTR Services. All doxy.me signed consent forms will be saved as PDF files within our study records. Signatures on the consent form may be obtained electronically via REDCap/doxy.me. To minimize concerns of errors/compliance with execution, Doxy.me will be the primary mode of eConsent with REDCap serving as a backup method in case there are system compatibility or end user concerns experienced. Participants will be encouraged to print and/or save a copy for their resource. If they do not have the ability to do so, a copy of the executed ICF will be provided to them at their next in-person visit or mailed per their preference.

No undue coercion or influence will be utilized for recruitment. The amount of compensation subjects may receive is nominal. All possible subjects will be treated the same. All patients that may screen fail or choose not to participate in the study will not have their standard of care altered or lose access to care.

10.0 Study Design / Methods

| Schedule of Events | Screening Call | In-Person Baseline Visit ^a | Monthly Call (Months 1,2,4,5,7,8,10,11) After Baseline* | Appointment Reminders (15 Days & 2 Days Before 3, 6, 9 Month Visit)** | Post 3, 6, 9 Month Visit ^a | Appointment Reminders (15 Days & 2 Days Before Post 12 Month Visit) | Post 12 Month Visit ^a |
|--|--|---------------------------------------|---|---|---------------------------------------|---|----------------------------------|
| Participation Assessment | X | | | | | | |
| Informed Consent & HIPAA | | X | | | | | |
| Steps To Care Intake Assessment Form | | X | | | | | |
| Steps To Care Reassessment Form | | | X | | X | | X |
| Participant Completed Assessments: Healthcare Resource Use Survey, Test of Functional Health Literacy | | X | | | | | |
| MacArthur Ladder, Experiences of Discrimination (EOD) measure | | X | | | | | X |
| LupusPRO | | X | | | X | | X |
| Medication Adherence Diary Review | | X | | | X | | X |
| Participant Completed Assessments: Perceived Stress Survey, Social Support Survey & Modified Picker Survey, Patient-Centered Care Questionnaire | | X | | | | | X |
| Appointment Reminder Calls | | | | X | | X | |
| Patient Satisfaction with Interpersonal Relationship with Navigator (PSN-I) survey | | | | | | | X |
| As Needed | | | | | | | |
| 1 Week F/U Call After Medication Change | Medication changes can occur at any time during the study. Medications to be included are those prescribed for your SLE. | | | | | | |

*Monthly Call window = +/- 7 calendar days.

**Appointment Reminder window = +/- 2 business days.

α All in person visits can be done in clinic or remotely via doxy.me

Screening:

PN will assess patient willingness to participate in the study as well as eligibility via a phone call, remote visit, in person at their clinic appointment, or once stable during an inpatient hospital stay.

Baseline In Person or Remote Visit:

Upon enrollment (Baseline visit) and signing of informed consent and HIPAA authorization, the PN will provide the following questionnaires, surveys and diaries:

- 1) Steps to Care Intake Assessment Form,
- 2) Healthcare Resource Use Survey,
- 3) LupusPRO survey,
- 4) Test of Functional Health Literacy,
- 5) Medication Adherence Diary,
- 6) Perceived Stress Survey,
- 7) Social Support Survey & Modified Picker Survey Patient-Centered Care Questionnaire,
- 8) Experiences of Discrimination (EOD) measure,
- 9) MacArthur Scale of Subjective Social Status (MacArthur Ladder).

Post 3, 6, & 9 Month In Person or Remote Visits:

- 1) Medication Adherence Diary review,
- 2) Steps to Care Reassessment Form,
- 3) LupusPRO survey.

Post 12-Month In Person or Remote Visit:

- 1) Medication adherence diary review,
- 2) Steps to Care Reassessment Form,
- 3) LupusPRO Survey,
- 4) Perceived Stress Survey,
- 5) Social Support Survey,
- 6) Modified Picker Survey Patient-Centered Care Questionnaire,
- 7) Experiences of Discrimination (EOD) measure,
- 8) MacArthur Scale of Subjective Social Status (MacArthur Ladder).

Monthly Phone Calls post signing of informed consent:

- 1) Steps to Care Reassessment Form

The PN will contact enrolled patients to provide appointment reminders. Contacts can be via phone, text, email, or MyChart as preferred by participant. These appointments are not only standard of care rheumatology visits but also associated to the research study in question. These contacts will be completed 15 days and 2 days prior to rheumatology clinic visit.

Additionally, the PN will call the patients one week following any changes in medications for their SLE (per primary Rheumatologist or patient reported) and will ensure patient has filled in proper

information on their Medication Adherence Diary during that contact. The PN will respond to phone calls from participating patients for health and general questions, notifying the appropriate medical provider when necessary and documenting all patient-initiated calls in the EMR. The PN will assess whether the patients' basic needs are being met (i.e. are there adequate resources for food, housing, medications, etc.) and make referrals for support services as needed (to include referrals for dietary modification, smoking cessation, exercise, obesity prevention, psychiatry, and substance abuse).

For each of these in-person visits with surveys, participants will be compensated \$10 (for a total of \$50.00 over 12 months of participation). Compensation will be delivered via ClinCard. The in-person PN visits will be planned in conjunction with scheduled outpatient clinic visits.

For the Usual Care Group only: As stated above, in order to properly obtain data, while minimizing risk to patients in this study, the study staff will only utilize data for those patients that have already enrolled in the Division of Rheumatology Core Center for Clinical Research (CCCR; Pro21985). These patients will have provided properly executed HIPAA authorization to utilize Protected Health Information through the CCCR for optional research portions of the CCCR study (see General Comments of IRB application to review CCCR HIPAA Authorization). Data on healthcare utilization and adherence to prescribed medications based on pharmacy records would be collected on the Usual Care group as part of standard quality of care monitoring, which are allowed to be collected through the CCCR; Pro21985. This data will be provided through a formal request process, reviewed by the executive committee of the CCCR, and provided to this study's staff via this request. Note that this group of patients (Usual Care) will not have a formal informed consent process completed and executed as only analysis of data already collected for standard of care is necessary and falls under the HIPAA Authorization for the CCCR.

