4.0 Study Endpoints

Improvement in Medication Adherence, Improvement in patient-reported lupus-specific disease status (measured by the LupusPRO), Improvement in Adherence with Primary Care / Specialty Care Visits, Lab and other Study Appointments.

Racial Discrimination will be measured using the validated 9-item Experiences of Discrimination (EOD) measure, which includes an index of racial discrimination experiences ever experienced. The EOD is a widely used and validated measure of racial discrimination. This short, self-report instrument is based on a prior instrument used in the Coronary Artery Risk Development in Young Adults (CARDIA) study validated in AA and Latino participants and has been previously used for measuring experiences of racial discrimination in AA women with SLE. (11).

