12.0 Data Management

The MUSC CCCR Patient Resource Core (Pro00021985) will act as an honest broker for the provision of clinical data of patients that fit criteria and are already enrolled in the CCCR study. The clinical data provided to the PN and PI of this study will include all data listed in sections 4.0 & 10.0 and will be provided to study staff de-identified. The data provided will only include 25 patient data sets for the "Usual Care" group that has not had contact with the patient navigator and serves as the control group for this study.

Analyses will be primarily descriptive in nature. Means, standard deviations, medians, inter-quartile ranges, and proportions will be reported on each outcome of interest, as appropriate. These statistics will be reported at baseline, 3 months, 6 months, and at 12 months for the primary outcome measure (Medication Adherence) and all secondary outcome measures. The secondary outcome measures are 1) Adherence with Primary Care and Specialty Care Visits, 2) Adherence with Lab and other Study Appointments, 3) Healthcare Utilization, 4) Disease-related Damage, 5) Corticosteroid Use and 6) Patient-Reported Outcomes.

In addition to results reported by our site, we will report results from our collaborating site, University of Alabama at Birmingham (UAB), during their implementation of the LPNP protocol.

Analyses will include estimates of site to site variability utilizing a combined MUSC and UAB dataset. All data sharing will be de-identified and maintained on MUSC's supported REDCap platform. Shared data and analyses were included in the Scope of Work executed by NIH subaward funding of 3P30AR072582-03S1, Improving Minority Health in Rheumatic Diseases.

Although this is not a randomized trial, we will use statistical methods such as propensity score weighting (36) to gain an understanding of how the use of PNs improves outcomes (e.g. medication adherence) when compared to usual care. Generalized linear mixed models will be used in conjunction with propensity score weighting to compare treatment group outcomes and estimate relevant effect sizes while adjusting for relevant baseline covariates (e.g. age, SLEDAI) and accounting for repeated measures within patients over time.

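### Baseline medication adherence is promised, but the navigator group has no stated source or look-back for it: its diary is first issued at the baseline visit

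*Combined protocol and SAP*

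**What the plan says.** Section 4.0 lists "Improvement in Medication Adherence" first among the endpoints, without instrument, unit, formula or time window. Section 12.0 makes adherence the primary outcome and commits to a baseline figure: "These statistics will be reported at baseline, 3 months, 6 months, and at 12 months for the primary outcome measure (Medication Adherence".

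For the navigator group, Section 10.0 introduces the diary at the baseline visit: "Upon enrollment (Baseline visit) and signing of informed consent and HIPAA authorization, the PN will provide the following questionnaires, surveys and diaries". The diary is item 5 of the list that follows. In the text lists, "Medication Adherence Diary review" first appears at the month 3, 6 and 9 visits and then again at month 12. The schedule of events, however, already marks a review at baseline: "Medication Adherence Diary Review | | X | | | X | | X". Section 9.0 adds: "No study procedures will be performed prior to obtaining written informed consent".

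For the comparison group, Section 10.0 names another source: "Data on healthcare utilization and adherence to prescribed medications based on pharmacy records would be collected on the Usual Care group". The documents do not say whether pharmacy records are also used for navigator patients.

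Table 1 in Section 3.0 lists the diary among the programme's own means of encouraging adherence. Section 12.0 states that the study is not randomised. It plans propensity weighting with generalised linear mixed models and gives age and SLEDAI as example covariates.

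**The concern.** An improvement endpoint needs a starting value measured before the intervention acts. A diary issued at the baseline visit holds no prospective entries from before that visit. Its first reviewed content, at month 3, was recorded while the patient was receiving navigator calls and using the diary, which is itself part of the programme. Taking month 3 as the start would hide any early navigator effect, although the plan does not propose to do so.

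The group comparison is also at stake. Navigator patients are consenting volunteers, while usual-care patients are selected from records. Adherence before the index date is a likely strong confounder of later adherence. If it is not measured on a common basis, neither the weights nor the model can account for it directly. The pilot is meant to supply preliminary effect estimates and sample-size inputs for a definitive trial (Section 12.0), and both would carry the problem forward.

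**Working it through.** **1. Order of events in the navigator group (Sections 9.0, 10.0 and Table 1).**
- Before the baseline visit: no study procedure, and no diary.
- At the baseline visit: consent, then the diary is issued. The schedule also marks a review, but the text list for this visit does not.
- Months 1 and 2: navigator calls.
- Month 3: first diary review in the text.

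So the diary has no stated pre-navigation content, and the baseline review mark has nothing described for it to review.

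**2. Other stated entry-time information on adherence.** Inclusion criterion 5 (Section 5.0) accepts a missed visit, self-reported non-adherence or new diagnosis. Self-reported non-adherence is one of three alternative routes, and no score is given for it. Pharmacy records are stated for usual care only, and no look-back or index date is given there either. Prior adherence is not among the named covariates.

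**3. The plan's own figure.** Section 12.0 claims more than 80% power for moderate differences in adherence, with 25 per group and two-sided alpha 0.05. It cannot be reproduced strictly because no number is attached to moderate. With an assumed standardised difference of 0.5 and one follow-up value, power = Φ(0.5/√(2/25) − 1.96) = Φ(−0.19) = 42% (41% with the noncentral t). Power of 80% needs (1.96 + 0.84) × √(2/25) = 0.79 SD. This does not decide the point, but it gives a scale for step 4.

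**4. What a baseline value is worth (assumed inputs).** Take the mean of three follow-up values (months 3, 6 and 12), compound symmetry with correlation ρ, and a difference of 0.5 SD. Without baseline, v = (1 + 2ρ)/3. With baseline as covariate, v = (1 + 2ρ)/3 − ρ². Power = Φ(0.5/√(2v/25) − 1.96).

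| ρ | v without | v with | Power without | Power with |
|---|---|---|---|---|
| 0.3 | 0.533 | 0.443 | 68% | 76% |
| 0.5 | 0.667 | 0.417 | 58% | 78% |
| 0.7 | 0.800 | 0.310 | 51% | 89% |

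An unadjusted change score has v = (1 + 2ρ)/3 + 1 − 2ρ, which gives 45%, 58% and 80%. It is never better than using baseline as a covariate.

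For a single follow-up value, baseline adjustment cuts residual variance by ρ²: 0.3² = 9%, 0.5² = 25%, 0.7² = 49%.

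**5. Bias from an unmeasured prior difference (assumed inputs).** With equal variances before and after, the carried-over difference is ρ × gap. For a gap of 10 percentage points: 0.3 × 10 = 3, 0.5 × 10 = 5, 0.7 × 10 = 7 points. In standardised terms, a gap of 0.25 to 0.5 SD leaves 0.25 × 0.3 = 0.075 to 0.5 × 0.7 = 0.35 SD.

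**The case against.** A reader might infer that a baseline value cannot exist, or that improvement can be neither shown nor adjusted for. The documents do not support either reading.

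- The diary's format is not described, so a recall section is neither stated nor excluded. The intake form and the resource-use survey given at baseline are not reproduced.
- Neither Section 4.0 nor Section 12.0 ties the outcome to the diary. Pharmacy records for navigator patients are not ruled out, and Section 17.0 describes all non-survey data as part of standard care.
- The consent rule bars procedures before consent. It does not bar retrieving earlier records after consent.
- The covariate list in Section 12.0 is open, and a comparison with usual care on post-baseline levels remains possible.
- The analyses are mainly descriptive, in a feasibility pilot. Both groups must meet criterion 5, which may narrow any gap in prior adherence.
- The bias figures assume no help from weights or other covariates, and pharmacy coverage measures adherence with error, so adjustment would not remove all of the bias.

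All of this stands, and it limits the point to an unspecified source. It does not dissolve it. A team following the text would have only the diary for navigator patients, and nothing in the text gives that diary a pre-navigation value.

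**Conclusion.** The point holds as a gap in the plan, not as an impossibility. Section 12.0 promises baseline adherence, but for the navigator group no source, look-back or definition is given. The one stated instrument starts at the baseline visit and belongs to the intervention. The schedule and the text list for that visit disagree and must be reconciled. As written, within-patient change from baseline and adjustment for pre-index adherence lack support in a comparison that depends on adjustment.

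The size for this trial is unknown. The 3 to 7 points of bias rest on an assumed 10-point gap, ρ of 0.3 to 0.7, equal variances and no help from other covariates. The 9% to 49% variance reduction rests on the same ρ range and a single follow-up value. The power figures add an assumed 0.5 SD effect and compound symmetry, and they ignore any loss of precision from weighting. They are illustrations, not estimates. The change is worth making before analysis because it is cheap and concerns the primary outcome.

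**What to change.** - Define baseline adherence as pharmacy-record coverage of prescribed SLE medication over one look-back, for example six months, in both groups. The window ends at the baseline visit for navigator patients and at a defined index date for usual care. Retrieve navigator records after consent, under an authorization that covers them.
- Report this as the baseline statistic in Section 12.0, and enter it in the propensity score and the mixed model.
- Compute any change score only against follow-up adherence from the same pharmacy-record measure, in both groups. A pharmacy baseline set against diary follow-up would mix two instruments. Keep the diary as a supportive or process measure.
- For newly diagnosed patients with no prior prescription period, report follow-up level and include an indicator in the model.
- Relabel the baseline schedule mark *diary issued*.

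The cost is protocol and analysis wording, a defined look-back in the pharmacy request already planned for usual care, and baseline and follow-up retrieval for 25 consented patients. Whether their authorization covers this is not visible in the documents and must be checked. Newly diagnosed patients would contribute no change score.
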